12.4. Appendix 4: Study Phases and Treatment Emergent Adverse Events

12.4.1. Study Phases

Assessments and events will be classified according to the time of occurrence relative to the start date of the study treatment.

Study Phase	Definition
Pre-Treatment	Date/Time < Study Treatment Dose Date/Time (Period 1)
On-Treatment	Study Treatment Dose Date/Time (Period 1) ≤ Date/Time

12.4.1.1. Study Phases for Concomitant Medication

Study Phase	Definition
Prior	If medication end date is not missing and is before 7 days prior to screening visit
Concomitant	Any medication that is not a prior For period specific concomitant medications, Refer to Section 12.6.1 for period definitions

NOTES:

- Please refer to [Appendix 7](#): Reporting Standards for Missing Data for handling of missing and partial dates for concomitant medication. Use the rules in this table if concomitant medication date is completely missing.

12.4.2. Treatment Emergent Flag for Adverse Events

Flag	Definition
Treatment Emergent	
 • If the AE is on-treatment, then the AE is treatment emergent. • Refer to Section 12.6.1 for period definitions.

NOTES:

- Time of study treatment dosing and start/stop time of AEs should be considered, if collected.

12.5. Appendix 5: Data Display Standards & Handling Conventions

12.5.1. Reporting Process

Software	

 The currently supported versions of SAS software will be used. R may be used for Stage 2 QC purposes. 	
Reporting Area	
HARP Server	: UK1SALX00175
HARP Compound	: arenv/arprod/gsk3858279/mid209973/
Analysis Datasets	

 Analysis datasets will be created according to Legacy GSK A&R dataset standards. 	
Generation of RTF Files	

 RTF files will be generated for Interim SAC (if performing) and final SAC/AAC tables. 	

12.5.2. Reporting Standards

General	

 The current GSK Integrated Data Standards Library (IDSL) will be applied for reporting, unless otherwise stated (IDSL Location: https://spope.gsk.com/sites/IDSLLibrary/SitePages/Home.aspx): 
 4.03 to 4.23: General Principles 5.01 to 5.08: Principles Related to Data Listings 6.01 to 6.11: Principles Related to Summary Tables 7.01 to 7.13: Principles Related to Graphics 	
Formats	

 GSK IDSL Statistical Principles (5.03 & 6.06.3) for decimal places (DP's) will be adopted for reporting of data based on the raw data collected, unless otherwise stated. Numeric data will be reported at the precision collected on the eCRF. The reported precision from non eCRF sources will follow the IDSL statistical principles but may be adjusted to a clinically interpretable number of DP's. 	
Planned and Actual Time	

 Reporting for tables, figures and formal statistical analyses: 
 Planned time relative to dosing will be used in figures, summaries, statistical analyses and calculation of any derived parameters, unless otherwise stated. The impact of any major deviation from the planned assessment times and/or scheduled visit days on the analyses and interpretation of the results will be assessed as appropriate. Reporting for Data Listings: 
 Planned and actual time relative to study drug dosing will be shown in listings (Refer to IDSL Statistical Principle 5.05.1). Unscheduled or unplanned readings will be presented within the subject's listings. 	
Unscheduled Visits	

 Unscheduled visits will not be included in summary tables and/or figures. All unscheduled visits will be included in listings and determination of PCIs. 	
Descriptive Summary Statistics	
Continuous Data	Refer to IDSL Statistical Principle 6.06.1

Categorical Data	N, n, frequency, %
Graphical Displays	
•	Refer to IDSL Statistical Principles 7.01 to 7.13.

12.5.3. Reporting Standards for Pharmacokinetic

Pharmacokinetic Concentration Data	
PC Windows Non-Linear (WNL) File	PC WNL file (CSV format) for the non-compartmental analysis by Clinical Pharmacology Modelling and Simulation function will be created according to VQD-GUI-000722 (6.0). Note: Concentration values will be imputed as per VQD-GUI-000722 (6.0).
Descriptive Summary Statistics, Graphical Displays and Listings	Refer to IDSL PK Display Standards. Refer to IDSL Statistical Principle 6.06.1. Note: Concentration values will be imputed as per VQD-GUI-000722 (6.0) for descriptive summary statistics/analysis and summarized graphical displays only.
NONMEM/Pop PK File	Not applicable.
NONMEM/PK/PD File	PK/PD file (CSV format) for the PK/PD analysis by Clinical Pharmacology Modelling and Simulation function will be created according to the data specification detailed in Section 12.9.1 Pharmacokinetic/Pharmacodynamic Dataset Specification.
Pharmacokinetic Parameter Derivation	
PK Parameter to be Derived by CPMS	The following PK parameters will be derived by CPMS: 
• AUC(0-t), AUC(0-7), Cmax, tmax and tlast.
Pharmacokinetic Parameter Data	
Is NQ impacted PK Parameters Rule Being Followed	Yes, refer to SOP_314000.
Descriptive Summary Statistics, Graphical Displays and Listings	Refer to IDSL PK Display Standards. Refer to VQD-GUI-000722 (6.0).

12.5.4. Reporting Standards for Target Engagement

Target Engagement Concentration Data	
Descriptive Summary Statistics, Graphical Displays and Listings	Refer to IDSL PK Display Standards. Refer to IDSL Statistical Principle 6.06.1. Note: Concentration values will be imputed as per VQD-GUI-000722 (6.0) for descriptive summary statistics/analysis and summarized graphical displays only. NQ values for Free CCL17 will be set to ½ LLQ and subsequent valid concentrations will be retained. Median will be imputed for missing baseline values. LLQ value will be imputed for baseline values equal to zero.

Target Engagement Parameter Derivation	
TE Parameter to be Derived by CPMS	
• None
TE Parameter to be Derived by Programmer	The following TE parameters will be derived by programmer: 
• Cmin, tmin, BL, percentage reduction, maximum percentage reduction for free CCL17• Cmax, tmax, BL, fold increase, maximum fold increase for total CCL17
Target Engagement Parameter Data	
Is NQ impacted PK Parameters Rule Being Followed	Yes, refer to SOP_314000.
Descriptive Summary Statistics, Graphical Displays and Listings	Refer to IDSL PK Display Standards. Refer to VQD-GUI-000722 (6.0).

12.6. Appendix 6: Derived and Transformed Data

12.6.1. General

Multiple Measurements at One Analysis Time Point	

 Mean of the measurements will be calculated and used in any derivation of summary statistics but if listed, all data will be presented. Participants having both High and Low values for Normal Ranges at any post-baseline visit for safety parameters will be counted in both the High and Low categories of “Any visit post-baseline” row of related summary tables. This will also be applicable to relevant Potential Clinical Importance summary tables. 	
Study Period	

 The start date of Period [1/2/3] is the dosing Day 1 date for that period. The end date of Period [1/2] is the Day -1 date for the subsequent period. The end date for Period 3 and Period[1/2] if no subsequent period follows, will be the final follow up visit date, or if applicable, study withdrawal date, whichever date is earlier. 	
Study Day / Period Day	

 Study day is derived with respect to the very first dose date (Period 1): 
 Ref Date = Missing → Study Day = Missing Ref Date < Dose Date → Study Day = Ref Date – Dose Date Ref Date ≥ Dose Date → Study Day = Ref Date – (Dose Date) + 1 Period day is derived with respect to the dose date during that period: 
 Ref Date = Missing → Period Day = Missing Ref Date < Period Start Date → Period Day = Ref Date – Period Dose Start Date Ref Date ≥ Period Start Date → Period Day = Ref Date – (Period Dose Start Date) + 1 	

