PainCart			X	X		X	X			Day 1 pre-dose performed twice (baseline) Day 1 performed at 1 and 3 hours post start of IV infusion. Other days performed twice ~2 hours apart at approximately the same time of day in each study period. Day 15 - heat pain detection assessment associated with UVB test performed on normal skin only. Participants not receiving UVB application will not undergo UVB heat pain detection test on irradiated skin. All other paincart assessments including heat pain detection performed on normal skin will still be assessed. See Appendix 7 for details of testing
UVB application		X			X					UVB application (2 x MED) will be performed 24hr (\pm 2hr) prior to start of infusion on Day 1. UVB application (2 x MED) on Day 7 will be performed 24hr (\pm 2hr) prior to PainCart assessment on Day 8. UVB application only applies to those in the UVB-MITT population.

Procedure	Study periods 1, 2, 3 (Days)								Early Withdrawal	Notes
	-2	-1	1	2	7	8	15	25		
AE review	X**	X	<=====→						X	
SAE review	X**	X	<=====→						X	
Concomitant medication review	X**	X	<=====→						X	
Blood samples for PK and PD			X	X		X	X		X	Day 1: pre-dose, 1hr, 3hr post-start of IV infusion. On other days samples taken prior to 1 st PainCart assessment.
Blood sample for immunogenicity			X			X			X	Day 1: pre-dose. Day 15: prior to 1 st PainCart assessment.

** If subjects are not UVB-MITT participants, optional admission will be on Day-1 with Day-2 SARS-CoV-2 test performed on Day-1.

- The timing and number of planned study assessments, including safety, pharmacokinetic, pharmacodynamic assessments may be altered during the course of the study based on newly available data to ensure appropriate monitoring.
- Any changes in the timing or addition of time points for any planned study assessments as the result of emerging pharmacokinetic/pharmacodynamic data from this study must be documented and approved by the relevant study team member and then archived in the sponsor and site study files but will not constitute a protocol amendment. The Competent Authority (CA) and ethics committee (EC) will be informed of any safety issues that constitute a substantial amendment and require alteration of the safety monitoring scheme or amendment of the informed consent form (ICF). The changes will be approved by the CA and the EC before implementation.
- The planned study assessments on Day 7 (UVB-MITT population only), 8, 15 and 25 may be performed within a ± 24hr window.

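### SAP 12.6.1 bounds study periods by calendar date, so an adverse event that starts on Day 1 before the Period 2 or 3 infusion is tabulated under an infusion not yet given, or falls in no period

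*SAP*

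**What the plan says.** SAP 12.6.1 defines periods by date, with no clock time. For the start: "The start date of Period [1/2/3] is the dosing Day 1 date for that period". For the end of the first two periods: "The end date of Period [1/2] is the Day -1 date for the subsequent period".

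SAP 12.4.1 works in date and time, but has one boundary for the whole study. On-treatment is "Study Treatment Dose Date/Time (Period 1) ≤ Date/Time", with no restart at the Period 2 or Period 3 dose.

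SAP 12.4.2 then states "If the AE is on-treatment, then the AE is treatment emergent" and, for period allocation, "Refer to Section 12.6.1 for period definitions". A note to the same table adds: "Time of study treatment dosing and start/stop time of AEs should be considered, if collected". It does not say how times change the period to which an event is allocated.

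SAP 8.1 restricts adverse-event analyses to on-treatment events. In SAP 12.11.7, safety tables are by period unless stated otherwise, and Table 3.03 presents placebo, GSK3858279 and total columns. The same section gives an attribution rule for liver events only (Table 3.23): the treatment being received at the time or, in washout, the last one received. General adverse events have no equivalent rule.

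SAP 5.1 lists two sequences, A/P/P and P/A/A. Protocol 1.3.2 schedules two baseline PainCart runs before the infusion on Day 1 of every period and, for UVB participants, irradiation about 24 hours before it.

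**The concern.** The hours before each infusion are not empty. Every participant completes two PainCart runs, and UVB participants carry a burn about a day old. An event with onset in that window cannot have been caused by the infusion that follows.

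In Periods 2 and 3 the on-treatment phase is already open, so such an event is flagged treatment emergent whatever the clock says. The date rule then gives it to the period whose dose has not yet been given. If a programmer uses the times instead, the previous period closed on Day -1 and the new one has not begun, so the event has no period and no clear treatment column. Two programmers could follow the SAP in good faith and produce different tables.

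Safety is the only objective besides the primary one that is not labelled exploratory, and the adverse-event tables belong to the reduced SAC package. Table 3.03 is where a reader compares drug with placebo.

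**Working it through.** No figure in the plan needs reproducing; this is a check of classification rules.

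**Test case.** Onset at 08:00 on Day 1 and infusion at 10:00, with doses 28 days apart (illustrative times; 28 days is the minimum washout). The treatment column is taken to follow from the period, because no other rule is given for general adverse events.

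**Rules compared.**
- (a) 12.6.1 as written, dates only.
- (b) Period start by dose time, following the 12.4.2 note, with the Day -1 end date kept.
- (c) Each period from its dose date/time to just before the next dose date/time.

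| Sequence | Pre-dose event on Day 1 of | (a) Date rule | (b) Time note, Day -1 end | (c) Dose to dose |
|---|---|---|---|---|
| A/P/P | Period 1 | excluded | excluded | excluded |
| A/P/P | Period 2 | Period 2, placebo | no period | Period 1, GSK3858279 |
| A/P/P | Period 3 | Period 3, placebo | no period | Period 2, placebo |
| P/A/A | Period 1 | excluded | excluded | excluded |
| P/A/A | Period 2 | Period 2, GSK3858279 | no period | Period 1, placebo |
| P/A/A | Period 3 | Period 3, GSK3858279 | no period | Period 2, GSK3858279 |

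Period 1 is the same under all three rules. Comparing (a) with (c), the treatment changes only in the Period 2 rows. In Period 3 the preceding treatment is the one about to be repeated, so only the period differs.

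**Possible size of the treatment-column error.**
- About 18 UVB participants are planned (Protocol 4.2), taken here as the maximum. One Period 2 session each gives 18 × 1 = 18 sessions.
- The documents give no rate of pre-dose events. Assumed range: 5%, 10% or 20% of sessions.
- Mislabelled events: 18 × 0.05 = 0.9; 18 × 0.10 = 1.8; 18 × 0.20 = 3.6.
- The two allocation patterns are equally likely, so about half of these fall in P/A/A: 9 × 0.05 = 0.45; 9 × 0.10 = 0.9; 9 × 0.20 = 1.8. They would stand under GSK3858279 in participants given only placebo so far.
- The other half fall in A/P/P and would stand under placebo in participants whose only product so far was GSK3858279.

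These counts cover UVB participants only. The others also complete two baseline PainCart runs, again with no stated event rate.

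**The case against.** The strongest reply is that the 12.4.2 note already requires dosing and onset times to be considered. If times are collected, no event need be charged to a later infusion. If they are not, Day 1 events cannot be split around the dose in any period. This stands in part: attribution to the coming infusion is the literal result of 12.6.1, not a certainty. But the note supplies no allocation rule, and with the Day -1 end date kept it leaves the event in no period. It also leaves the treatment-emergent flag unchanged in Periods 2 and 3.

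A reader might infer that leaving out pre-dose events in Period 1 is itself an error. The documents do not support that. Protocol 8.2.1 collects adverse events from the start of study intervention and sends earlier occurrences to medical history.

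A reader might also infer that the rule dilutes the drug-placebo contrast, or produces a rise in events after Period 1. Both are possible; neither is demonstrated. Without a pre-dose event rate no rise can be shown. If misplaced events split evenly between the columns, the absolute difference is not shifted.

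The window is also short. UVB reactions with onset on Day -1 stay in the previous period, so only the hours before infusion on Day 1 are in dispute. Listing 16 shows every adverse event, which lets a careful reader trace individual cases.

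**Conclusion.** The point holds, with limited reach. The date-only boundary in 12.6.1 and the single date/time boundary in 12.4.1 do not fit together. For an event on Day 1 before infusion in Period 2 or 3, they give either a wrong period or none.

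The treatment column is wrong in Period 2 only. Counting Period 3 events as mislabelled by treatment would be tempting but wrong, given the sequences A/P/P and P/A/A.

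The estimate of 0.9 to 3.6 events rests on the assumed 5% to 20% rate and on 18 UVB participants reaching Period 2. SAP 1.1 records that the study was terminated for futility, and the documents do not give the number who reached Period 2. They also do not confirm that adverse-event onset times are collected. The consequence is confined to descriptive adverse-event tables; the primary PainCart analysis does not use these rules.

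**What to change.** In SAP 12.6.1, for adverse-event allocation, define each period as running from that period's dosing date/time to just before the next period's dosing date/time. Keep the existing end rule for the last period. A pre-dose Day 1 event in Period 2 or 3 then goes to the last treatment received, in line with the SAP's own rule for liver events.

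State a default for Day 1 events with no onset time, for example keeping them in the new period with a footnote.

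Optionally, flag events with onset between admission and infusion in the adverse-event listing, but leave them in the treatment columns. Moving them to a separate phase outside both columns is not advisable. It would contradict the dose-to-dose definition and could remove late drug events: Protocol 4.4 puts unbound CCL17 at only about 30% of baseline four weeks after dosing.

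The cost is minor SAP wording and programming. Infusion start and stop times are already recorded (SAP 12.6.2). Day 1 events without an onset time remain ambiguous.

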If participants prematurely discontinue the study, additional replacement participants may be randomized at the discretion of the Sponsor and in consultation with the Principal Investigator in order to ensure sufficient participants complete the study. Replacement participants will be assigned to the same treatment sequence as the participant they are replacing, at the discretion of the Sponsor and in consultation with the Principal Investigator.

Intervention Groups and Duration:

The study duration, including screening and follow-up will be approximately 6 months for all participants in the study:

Screening	Approximately 28 days prior to first dose.
Number of Participants	One Cohort of a maximum of 30 participants (N=30)
Study (Treatment) Period(s)	Will comprise of three study periods, investigating the difference between GSK3858279 (3mg/kg IV) and Placebo in the PainCart assessments. Each participant will be admitted to the unit either two days before dosing (Day-2, UVB-MITT participant) or one day before dosing (Day-1, non-UVB-MITT participant) on each study period. Participants will be dosed on Day 1 and discharged on Day 2 (except if, for medical reasons, participants need to stay longer). The participants will return for an outpatient visits on Day 7 (UVB-MITT participants only), Day 8 and Day 15. The participants will be contacted on Day 25 and asked about their general health.
Washout Period	Will be at least 4 weeks between doses for an individual participant.
Follow-Up	The participants will be contacted on Day 36 by telephone and asked about their general health. Approximately 56 days after the last study administration, a final follow-up visit will occur. If warranted, additional follow-up visits may be scheduled.

Data Monitoring or Other Committee:

There will not be a data monitoring committee or any other committee on this study.

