8.2.1. Time Period and Frequency for Collecting AE and SAE Information

- All SAEs will be collected from the start of intervention until the follow-up visit at the time points specified in the SoA (Section 1.3). However, any SAEs assessed as related to study participation (e.g., study intervention, protocol-mandated procedures, invasive tests, or change in existing therapy) or related to a GSK product will be recorded from the time a participant consents to participate in the study.
- All AEs will be collected from the start of study intervention until the follow-up visit at the time points specified in the SoA (Section 1.3).
- Medical occurrences that begin before the start of study intervention but after obtaining informed consent will be recorded on the Medical History/Current Medical Conditions section of the case report form (CRF) not the AE section.
- All SAEs will be recorded and reported to the sponsor or designee immediately and under no circumstance should this exceed 24 hours, as indicated in [Appendix 3](#). The investigator will submit any updated SAE data to the sponsor within 24 hours of it being available.
- Investigators are not obligated to actively seek AEs or SAEs after the conclusion of the study participation. However, if the investigator learns of any SAE, including a death, at any time after a participant has been discharged from the study, and he/she considers the event to be reasonably related to the study intervention or study participation, the investigator must promptly notify the sponsor.

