Phone contact to assess the participant's general health will be conducted as per the SoA, the investigator may invite the participant for a site visit at the investigator's discretion for additional follow-up, as required.

Overview of Study Design and Key Features

Figure 1 Study Design Schematic

[figure not shown]

Figure 2 Visit schematic

[figure not shown]
[figure not shown]

Figure 3 Study Period Details

Study Periods 1, 2 and 3

* Required only in UVB-MITT population

** Optional assessments/study day applicable to UVB-MITT volunteers only

Design Features	
 A screening visit can occur up to 28 days before study day 1. A SARS-CoV-2 PCR test and temperature check will be performed at screening visit, prior to any other screening procedure. Each study period lasts for approximately 4 weeks, with PainCart assessments occurring the first 2 weeks and wash out periods lasting approximately 4 weeks between treatment dosing in each period. For each study period, UVB application (2 x MED) will be performed 24hr (± 2hr) prior to start of infusion on Day 1 and Day 7 (24hr (± 2hr) prior to start of PainCart assessment on Day 8, for those participants enrolled into the UVB group. The PainCart assessments are performed twice on Day 1 before start of infusion (baseline readings) and performed twice again on Day 1 at 1 and 3 hours post start
------------------------	---

Overview of Study Design and Key Features							
	
of IV infusion. On days 2, 8 and 15, the PainCart assessment is performed twice, approximately 2 hours apart. On day 15 the UVB pain assessment will only be performed on normal skin, due to no UVB applied skin being applicable at that visit. The planned PainCart assessments on Day 2, 8 & 15 may be performed within a \pm 24hr window.
 
 • Participant replacements are permitted in the study. • A follow up phone call is scheduled on day 36 of study period 3 (approximately 6 weeks post dose) and a final follow up out-patient visit scheduled on day 56 (approximately 8 weeks post dose). • Participants will be stratified in to two strata based on whether they perform the PainCart assessments in the morning (AM) or the afternoon (PM). These strata will continue throughout the full duration of the study for the participant (e.g. if a participant performs their first PainCart assessment in the morning, they will perform their subsequent assessments in the morning too). 						

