12.2. Appendix 2: Schedule of Activities

12.2.1. Protocol Defined Schedule of Events

12.2.1.1. Screening and Follow-Up

Procedure	Screening (up to 28 days before Day 1)		Follow-up check 36 ± 4 days post last dose	Final follow-up 56 ± 4 days post-last dose	Notes
	Part 1	Part 2			
Out-patient visit	X	X		X	Optional in-clinic stay for participants at the discretion of investigator.
Phone call			X		AE collection - may be out-patient visit at discretion of Investigator for additional checks
Informed consent	X				
Severe acute respiratory syndrome SARS-CoV-2 PCR test	X			X	
Temperature check	X	X		X	
Inclusion and exclusion criteria	X				Recheck clinical status before randomization and/or 1st dose of study intervention.
Demography	X				
Full physical examination including height and weight.	X				Weight at screening is used for determination of dose
Fitzpatrick Skin Type	X				Assessments for UVB-MITT population only Assessment to determine applying MED application
Echocardiogram	X				
Medical history (includes substance usage)	X				Substances: Drugs, Alcohol, tobacco and caffeine
Current medical conditions	X				
HIV, Hepatitis B and C	X				
Haematology, clinical chemistry (include liver chemistries) and urinalysis	X			X	Including Troponin-T (hs)
NT-proBNP	X			X	
UrDrug, BrAlc	X			X	
12-lead ECG	T			X	T = Triplicate X = Single
Vital signs	X			X	

Procedure	Screening (up to 28 days before Day 1)		Follow-up check 36 ± 4 days post last dose	Final follow-up 56 ± 4 days post-last dose	Notes
	Part 1	Part 2			
PainCart training	[X]	[X]			May be performed during either part 1 or part 2 (not both)
Minimal Erythema Dose (MED) application		X			Assessments for UVB-MITT population only. Exposure to pre-determined 6 ascending doses of UVB radiation. MED application will be the final assessment on Part 1 of Screening and will only be completed after confirmation of eligibility from available results, e.g. lab data, echocardiogram results may not be available.
MED assessment		X			Assessments for UVB-MITT population only. 24 hours (± 2 hours) after UV exposure
AE/SAE review	X	X	X	X	

- An echocardiogram performed within 3 months prior to first dosing is acceptable for enrolment into the study
- MED determination performed within 6 weeks prior to first dosing is acceptable for enrolment into the study

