12.11.7. Safety Tables

Safety: Tables – All Safety Tables will be presented by Period unless stated otherwise.					
No.	Population	IDS / Example Shell	Title	Programming Notes	Deliverable [Priority]
Adverse Events (AEs)					
3.01.	Safety	AE1xo	Summary of All Adverse Events by System Organ Class and Preferred Term by Period	ICH E3 Present by Period Programming note: For interim analysis present AEs SOCs and PTs which have more than 2 subjects overall per period. i.e. at least two unique subjects in the Total column per period. Include footnote: Note: For interim, only AEs occurring in two or more subjects by period are reported.	IA 1 [1], IA 2 [2], SAC [3]
3.02.	UVB-Safety	AE1xo	Summary of All Adverse Events by System Organ Class and Preferred Term by Period – UVB Participants Only	ICH E3 Present by Period	SAC [1]
3.03.	Safety	AE1xo	Summary of All Adverse Events by System Organ Class and Preferred Term - Overall	ICH E3 Present Placebo, GSK3858279, Total Columns	SAC [1]
3.04.	Safety	AE5A	Summary of All Adverse Events by System Organ Class and Preferred Term and Maximum Intensity by Period	ICH E3	SAC [1]
3.05.	Safety	AE1xo	Summary All Drug-Related Adverse Events by System Organ Class and Preferred Term by Period	ICH E3	SAC [1]
3.06.	Safety	AE5A	Summary of All Drug-Related Adverse Events by System Organ Class and Preferred Term and Maximum Intensity by Period	ICH E3	SAC [1]
3.07.	Safety	AE3	Summary of Non-Serious Drug-Related Adverse Events by Overall Frequency by Period	PLS Requirement	SAC [1]

Safety: Tables – All Safety Tables will be presented by Period unless stated otherwise.					
No.	Population	IDSL / Example Shell	Title	Programming Notes	Deliverable [Priority]
3.08.	Safety	AE15	Summary of Common (>=5%) Non-serious Adverse Events by System Organ Class and Preferred Term (Number of Participant and Occurrences) by Period	FDAAA, EudraCT	SAC [1]
Serious and Other Significant Adverse Events					
3.09.	Safety	AE16	Summary of Serious Adverse Events by System Organ Class and Preferred Term (Number of Participants and Occurrences) by Period	FDAAA, EudraCT Produce if more than 5 SAEs are reported.	SAC [1]
3.10.	Safety	AE3	Summary of Serious Drug-Related Adverse Events by Overall Frequency by Period	PLS Requirement	SAC [1]

Safety: Tables – All Safety Tables will be presented by Period unless stated otherwise.					
No.	Population	IDSL / Example Shell	Title	Programming Notes	Deliverable [Priority]
Laboratory: Chemistry					

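### The SAP's period dates give Period 3 a longer adverse-event window (about 57 v 28 days at 4-week spacing), so by-period counts carry an expected upward bias in Period 3

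*SAP*

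**What the plan says.** SAP 12.6.1 sets the period dates. The start is the same for all three periods: "The start date of Period [1/2/3] is the dosing Day 1 date for that period". The end is not. For the first two periods, "The end date of Period [1/2] is the Day -1 date for the subsequent period". For the last, "The end date for Period 3 and Period[1/2] if no subsequent period follows, will be the final follow up visit date", or the withdrawal date if that comes first. The second rule also applies to Period 1 or 2 of anyone who stops early.

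The SAP's schedule of activities (12.2.1.1) places that visit late: "Final follow-up 56 ± 4 days post-last dose". The extra time is actively observed, since Protocol 8.2.1 states: "All AEs will be collected from the start of study intervention until the follow-up visit".

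These dates drive the adverse-event tables. SAP 12.4.1 gives the on-treatment phase no upper limit, and SAP 12.4.2 refers to 12.6.1 for the period definitions. The default in SAP 12.11.7 is "All Safety Tables will be presented by Period unless stated otherwise". By title, Tables 3.01, 3.02 and 3.04 to 3.10 are by period; Table 3.03 pools over periods by treatment. The SAP specifies neither a common onset window nor a rate per person-time.

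**The concern.** A count of participants with at least one event depends on how long they are watched. If one period is watched for longer, its count is expected to be higher with no change in underlying risk.

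The imbalance falls on a comparison that a reader is likely to make. SAP 5.1 lists two sequences, A/P/P and P/A/A. Every second active dose is therefore in Period 3, and every active participant in Period 3 is on a second dose. A reader looking for a repeat-dose effect would compare P/A/A in Period 2 with P/A/A in Period 3. The question is a natural one: Protocol 2.3.1 discusses hypersensitivity linked to anti-drug antibodies and describes infusion reactions in one monkey after repeated dosing.

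The displays are also not purely internal. SAP 12.11.7 marks Tables 3.08 and 3.09 for registry reporting.

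**Working it through.** **Inputs**
- Period start and end dates: SAP 12.6.1.
- Planned spacing: SAP 2.3 says "Each study period lasts for approximately 4 weeks, with PainCart assessments occurring the first 2 weeks". The protocol synopsis gives a minimum for the washout: "Will be at least 4 weeks between doses for an individual participant".
- Final follow-up: day 56 after the last dose, range 52 to 60.
- Adverse-event rate: not given in the documents. It is assumed below and ranged from 10% to 50% per 28 days.

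**Step 1. The SAP's own period length.** With a gap of g days, the next dose falls on Day g+1 and its Day -1 is Day g. Periods 1 and 2 therefore last g days, counted inclusively. At g = 28 this is 28 days, which reproduces the SAP's 4 weeks.

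**Step 2. Period 3.** Day 1 to 56 days after dosing is 56 + 1 = 57 days inclusive (53 to 61 over the visit window). The 4-week figure does not reproduce for Period 3.

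**Step 3. Ratio and expected count.** The ratio is 57/g. Under a constant daily rate, if a proportion p has an event in a period of g days, the expected proportion in Period 3 is 1 − (1 − p)^(57/g).

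| Gap g (days) | Periods 1 and 2 | Period 3 | Ratio (over ±4 days) | p = 30% becomes |
|---|---|---|---|---|
| 28 | 28 | 57 | 2.04 (1.89–2.18) | 52% |
| 35 | 35 | 57 | 1.63 (1.51–1.74) | 44% |
| 42 | 42 | 57 | 1.36 (1.26–1.45) | 38% |
| 49 | 49 | 57 | 1.16 (1.08–1.24) | 34% |

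At g = 28, values of p of 10%, 20% and 50% become 19%, 37% and 76%. Counting 56 against 28 elapsed days instead gives 1 − 0.7² = 51% for p = 30%. Period 3 stays longer for any gap under 57 days, about 8 weeks.

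**Step 4. Which gap is likely?** At 4-week gaps, participation is 28 (screening) + 28 + 28 + 56 = 140 days, or 4.6 months. The protocol's total of about 6 months (182.6 days) would imply gaps of (182.6 − 28 − 56)/2 ≈ 49 days. The documents support both ends of the table.

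**Step 5. If events cluster near dosing.** Let H = −ln(1 − p), and let a share f of H be tied to dosing and procedures and not recur after Day 28. Then H₃ = fH + (1 − f)H × 57/28. For p = 30%, the Period 3 proportion is 52% at f = 0, 42% at f = 0.5, 35% at f = 0.8 and 30% (no rise) at f = 1.

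**Step 6. Balance by treatment.** For one A/P/P and one P/A/A completer at 4-week gaps, active time is 28 + (28 + 57) = 113 days. Placebo time is (28 + 57) + 28 = 113 days.

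**The case against.** The strongest reply is that the planned treatment comparison is GSK3858279 against placebo, and the windows do not bias it. In each period both columns share the same rule. Pooled Table 3.03 is balanced when the sequences are 1:1 and completed (step 6). No first-versus-second-dose or trend analysis is specified, and the listings and onset dates let anyone rebuild the counts. Following the last dose to 56 days is itself reasonable: Protocol 4.4 reports drug levels below quantification after 8 weeks. All of this stands. It confines the problem to reading the by-period tables across periods.

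The size is also open. Four weeks is a minimum gap, and infusion, PainCart testing and the Day 7 UVB application all fall in the first 15 days. A doubling of time need not mean anything near a doubling of events.

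A reader might infer three stronger things, and the documents support none of them:
- **That a true repeat-dose rise could not be separated from the longer window.** The placebo columns in Periods 2 and 3 both come from A/P/P and undergo the same change of window. They give a concurrent reference, though an imprecise one (at most about 30/2 = 15 participants) that follows an earlier active dose.
- **That Period 3 is also watched more closely.** It gains the Day 36 call and the final visit. However, the next period's Day -2 and Day -1 event reviews fall inside Periods 1 and 2 and largely offset them.
- **That UVB exposure adds to the rise.** By application date, a UVB participant has 2, 2 and 1 applications in Periods 1, 2 and 3. That would push Period 3 down, not up.

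**Conclusion.** The point holds as a bias in cross-period reading. By rule, Period 3 is observed for longer, by a factor of about 2.0 at the planned 4-week spacing and 1.2 at 49-day gaps. The by-period adverse-event tables make no allowance for it. The direction of the expected bias is upward in Period 3 when there is no true period effect. The amount rests on an assumed event rate and on how many events start after the first 4 weeks. For a 30% incidence in 28 days, it ranges from no rise to about 52%. An observed rise is not guaranteed.

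Unequal windows can also arise within Periods 1 and 2, because early stoppers are followed to the final visit or withdrawal. SAP 1.1 records that the study was terminated at the futility analysis, so this may matter, but the documents do not say how many participants are affected.

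The primary endpoints are untouched. The change is worth making because it is cheap and removes a known bias from reported tables.

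**What to change.** In SAP 12.6.1 and 12.11.7, define a common onset window for by-period adverse-event counts. It could run, for example, from dosing on Day 1 to Day 28, or to the day before the next dose if earlier, and would apply to all three periods. Use it in Tables 3.01, 3.02 and 3.04 to 3.10.

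In each of those tables, add a late/follow-up column for every event with onset after the window, assigned to the last treatment received. The column must take late events from any period, including Periods 1 and 2 when the gap exceeds 28 days and participants who stop early. If it took only Period 3 events, some drug-related, serious or severe events would drop out of these tables. Keep Table 3.03 and the listings unrestricted.

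The cost is one onset flag, one column and a few lines of SAP text, with no change to data collection. The main Period 3 counts become smaller, with the later events shown beside them. These tables are due at the SAC milestone, so the wording should be settled before that run.
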